5.2. Patient Disposition

All randomized participants who discontinue the study/treatment will be identified, and a reason for their discontinuation will be given. The reasons for study/treatment discontinuations will be summarized by treatment using the Randomized Population and the Efficacy Population.

Comparison will be conducted using the Fisher's exact test. A listing of the reasons for study/treatment discontinuations will be generated for the Enrolled Population.

Reasons for discontinuation prior to randomization will also be summarized. A listing of the randomized treatment for this study will be provided.

5.3. Patient Characteristics

Demographic and baseline characteristics including but not limited to age (years), age groups (<25 , ≥ 25 and <40 years, ≥ 40 years; <65 years, ≥ 65 years and <75 years, ≥ 75 years), sex, ethnicity, race, country, region, weight (kg), body mass index (BMI: kg/m^2), BMI groups (<25 , ≥ 25 and <30 , ≥ 30 and <35 , and $\geq 35 \text{ kg}/\text{m}^2$), eGFR groups (estimated glomerular filtration rate based on the modified Modification of Diet in Renal Disease [MDRD] equation: ≥ 90 , <90 and ≥ 60 , <60 and ≥ 30 , and $<30 \text{ mL}/\text{min}/1.73 \text{ m}^2$), duration of diabetes (years), baseline substance use (alcohol, drug, tobacco and caffeine baseline use status), baseline systolic blood pressure, baseline diastolic blood pressure, baseline HbA1c (% and mmol/mol), baseline HbA1c groups ($<7\%$, $\geq 7\%$ and $<8.5\%$, $\geq 8.5\%$), fasting serum glucose (FSG: mmol/L and mg/dL), and HbA1c screening group (HbA1c $<8.5\%$ and $\geq 8.5\%$ at Visit 1) will be summarized by treatment group for the Efficacy Population, Randomized Population, and Safety Population. Comparisons of categorical variables between treatment groups will be assessed using a Pearson Chi-Square test. Comparisons of continuous variables between the treatment groups will be performed using a 1-way analysis of variance with treatment as the fixed effect. The by-patient listing of demographic and selected baseline characteristics will be provided for all randomized patients.

Number of randomized patients and number of randomized patients discontinued per investigator within country for each treatment group will be summarized. In addition, number of enrolled patients per investigator within each country will also be summarized.

5.4. Concomitant Medications

Concomitant medications used during the treatment period will be summarized by treatment groups and will be compared between treatment groups using Fisher's exact test for the Safety

Population. The percentages of patients who took concomitant medication will be summarized by treatment using Preferred Terms (PTs) nested within Anatomical Therapeutic Chemical (ATC) Level 3 codes. The concomitant medications will be ordered by decreasing frequency within each ATC level.

5.5. Treatment Adherence

Treatment adherence will be summarized using the EAS. For a given study participant, overall adherence for treatment period is based on the ratio of the total number of doses taken to the total number of required doses. CCI

Adherence to the dosing algorithm is required from Visit 3 (Randomization) up to Visit 20. The number and percentage of investigator prescribed doses that did not follow the algorithm recommended dose and the number and percentage of patient actual administration dose that did not follow the investigator prescribed dose will be provided.

Similar descriptive statistics will be provided for patients randomized to LY3209590 Algorithm 2 arm and took at least one study dose.

5.6. Protocol Deviations

Important protocol deviations (IPDs) defined as deviations from the study protocol that may compromise the data integrity and patients' safety will be summarized by treatment group for the Randomized Population and the Efficacy Population. The listing of IPDs for the Randomized Population will also be provided.

5.7. Primary Outcome and Methodology

The primary objective is to compare the HbA1c change from baseline to Week 26 between LY3209590 and insulin degludec and will be based on the primary estimand described below.

The primary estimand is the treatment differences in the change in HbA1c from baseline to 26 weeks for the targeted study population if all patients would adhere to the treatment without intercurrent events. The analysis data will include data up to the discontinuation of study treatment for the Efficacy Population with baseline and at least one non-missing postbaseline measurement. There may be missing values due to the early discontinuation of study treatment. The MMRM model will be used with the HbA1c changes at Week 6, 12, 16 and 26 (the primary endpoint) and the missing values will be imputed implicitly in the MMRM analysis under the assumption of missing at random. The MMRM model will include treatment (LY3209590 Algorithm 1, insulin degludec), country, visit, and treatment by visit interaction and the baseline value of the dependent variable as the fixed effects. The HbA1c is reported in unit of % and will be converted to the unit of mmol/mol using the following formula: HbA1c in mmol/mol = 10.93*HbA1c in % - 23.5 (<http://www.ngsp.org/ifccngsp.asp>). HbA1c analysis will be conducted based on both units.

In the MMRM model, the within-patient errors are modeled as an unstructured variance-covariance matrix. If the analysis fails to converge, the following variance-covariance matrix will be used (in order) until one converges:

1. Toeplitz with heterogeneity
2. autoregressive with heterogeneity
3. compound symmetry with heterogeneous variances
4. Toeplitz
5. autoregressive
6. compound symmetry without heterogeneous variances

The Kenward-Roger approximation will be used to estimate denominator degrees of freedom for the MMRM models. The following is an example SAS code:

```
proc mixed data=DATA;
  class TREATMENT STRATIFICATIONS VISIT PATIENT;
  model HbA1c=BASELINE TREATMENT STRATIFICATIONS VISIT
    VISIT*TREATMENT / solution ddfm=kr;
  repeated VISIT / subject=PATIENT type=un;
  lsmeans TREATMENT*VISIT/ pdiff cl alpha=0.1 om=DATA;
run;
```

The 2-sided 90% CI of the LS mean for individual treatment groups, treatment LS mean difference (LY3209590 Algorithm 1 versus insulin degludec) in the HbA1c change from baseline to Week 26 will be estimated. Similar analysis based on the above MMRM model will also be provided for the comparison between LY3209590 (by pooling LY3209590 Algorithm 1 and LY3209590 Algorithm 2) and insulin degludec.

With the primary estimand, LY3209590 Algorithm 1 will be declared noninferior to insulin degludec if the upper limit of the 2-sided 90% CI for the LS mean difference in the HbA1c change from baseline is below +0.4%.

A supportive estimand is the treatment differences in HbA1c change from baseline to Week 26 for the targeted study population regardless of the use of rescue medication or taking study medication. The analysis data will include all available data at Week 26 regardless of treatment disposition status for all randomized patients who took at least one dose of study treatment and have non-missing baseline. There will be missing endpoint due to early study discontinuation. The missing endpoint will be imputed by “return to baseline” imputation. Multiple imputations will be conducted and an analysis of covariance model including factors of treatment and country, and baseline HbA1c as covariates will be performed by imputation data set. Then, the inference will be based on bootstrap method.

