5.1. General Considerations

All data will be entered, verified, and archived at a contract research organization (CRO) external to Eli Lilly and Company (Lilly) and/or at Lilly. Data listings, summaries, and analyses will be performed by a CRO and/or by Lilly under the guidance and approval of statisticians at Lilly.

Statistical analysis of this study will be the responsibility of sponsor or its designee. Any change to the data analysis methods described in the protocol will require an amendment only if it changes a principal feature of the protocol. Any other change to the data analysis methods described in the protocol, and the justification for making the change, will be described in this SAP and/or the clinical study report(CSR). Additional exploratory analyses of the data will be conducted as deemed appropriate.

The following populations are defined for purpose of analysis:

Population	Description
Entered/Enrolled Population	All participants who sign the ICF
Randomized Population	All participants assigned to treatment, regardless of whether they take any doses of study treatment, or if they took the correct treatment. The participants previously randomized to LY3209590 Algorithm 2 will be pooled with the participants randomized to Algorithm 1 and all of these participants will be analyzed as one treatment group of LY3209590.
Efficacy Population	All participants randomized to either LY3209590 Algorithm 1 or insulin degludec and took at least 1 dose of study treatment. Participants will be analyzed according to the treatment they were assigned.
Safety Population	All participants randomly assigned to study intervention and who took at least 1 dose of study treatment. The participants previously randomized to LY3209590 Algorithm 2 will be pooled with the participants randomized to Algorithm 1 and all of these participants will be analyzed as one treatment group of LY3209590.
Pharmacokinetic Population	All randomized participants who received at least 1 dose of LY3209590 and have at least 1 evaluable PK sample.

Abbreviations: ICF = informed consent form; PK = pharmacokinetics.

Unless otherwise stated, the efficacy analyses will be conducted on efficacy analyses set (EAS) based on the Efficacy Population using the data up to the study treatment discontinuation

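### The supportive HbA1c estimand's patient set, read literally, includes dosed patients from the terminated Algorithm 2 arm, while the primary estimand compares Algorithm 1 with insulin degludec only

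*SAP*

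**What the plan says.** SAP 5.7 gives two estimands for HbA1c change to Week 26.

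- **Primary.** Data up to treatment discontinuation are used "for the Efficacy Population with baseline and at least one non-missing postbaseline measurement". The treatment levels are written out: "The MMRM model will include treatment (LY3209590 Algorithm 1, insulin degludec), country, visit, and treatment by visit interaction". Noninferiority is declared on this estimand, for Algorithm 1 against insulin degludec, with a margin of 0.4%.
- **Supportive.** "The analysis data will include all available data at Week 26 regardless of treatment disposition status", and this is done "for all randomized patients who took at least one dose of study treatment and have non-missing baseline". Missing Week 26 values are imputed by return to baseline and analysed by ANCOVA with treatment, country and baseline HbA1c. The treatment levels are not given.

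SAP 5.1 defines the populations. The Efficacy Population is "All participants randomized to either LY3209590 Algorithm 1 or insulin degludec and took at least 1 dose of study treatment". The Safety Population is "All participants randomly assigned to study intervention and who took at least 1 dose of study treatment"; for it, and for the Randomized Population, Algorithm 2 participants are joined with Algorithm 1 and "all of these participants will be analyzed as one treatment group of LY3209590". SAP 5.1 also sets a default: "Unless otherwise stated, the efficacy analyses will be conducted on efficacy analyses set (EAS) based on the Efficacy Population".

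**The concern.** The supportive paragraph cites no defined population. Apart from the baseline condition, its wording is close to the Safety Population, which contains Algorithm 2. The set restricted to Algorithm 1 and degludec, the Efficacy Population, is named for the primary estimand and not for this one.

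The purpose of the supportive estimand is to show what happens to the treatment difference when discontinuation and rescue are ignored and off-treatment data are counted. That is cleanest when only the intercurrent-event strategy and its data rule change. If Algorithm 2 patients also enter, the LY3209590 group changes as well. According to the rationale for the current protocol amendment, that arm was stopped because patient data-entry errors affected its dose recommendations and because investigator overrides confounded its evaluation. The treatment-policy counterpart of the Algorithm 1 claim would then be missing. Two programmers could also build different analysis sets from the same paragraph.

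**Working it through.** **1. The plan's own figures.** Protocol 9.2 assumes SD 1.1%, margin 0.4%, true difference 0 and two-sided alpha 0.1 (one-sided 0.05).

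- Per arm for 80% power: 2 × (1.1/0.4)² × (1.645 + 0.842)² ≈ 93.5, so 94.
- Power at 95 per arm: standard error 1.1 × √(2/95) = 0.160; 0.4/0.160 − 1.645 ≈ 0.86, so about 80.5%.
- Randomized: 190/0.8 = 237.5, so 238, or 119 per arm.

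These reproduce, and none depends on the point raised here.

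**2. The sets side by side.**

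| Set | Dose required | Algorithm 2 | Other condition |
|---|---|---|---|
| Primary analysis (SAP 5.7) | yes | excluded | baseline and a postbaseline value |
| Efficacy Population (SAP 5.1) | yes | excluded | none |
| Safety Population (SAP 5.1) | yes | pooled | none |
| Supportive analysis (SAP 5.7) | yes | not excluded | baseline |

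Dosed Algorithm 2 patients are a recognised group: SAP 5.5 plans separate adherence summaries for them. They were randomized and dosed, so any of them with a baseline value meets the supportive condition as written.

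**3. Does the default resolve it?** The default set (EAS) is the Efficacy Population with data up to last dose + 10 days, and it applies unless the SAP states otherwise. The supportive paragraph states its own patient set and its own data rule. The data rule clearly departs from the EAS. Whether the population part of the default survives is not said.

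**4. What the planned outputs allow.** Let A be the Algorithm 1 MMRM, B the pooled MMRM (also planned in SAP 5.7) and C a supportive analysis that includes Algorithm 2. Then C − A = (B − A) + (C − B). B − A is the effect of adding Algorithm 2 with the model and data rule held fixed. C − B is the change of strategy, model and imputation with the LY3209590 group held fixed. The supportive analysis for Algorithm 1 alone is not among the outputs.

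**5. Size, as illustration only.** The documents describe the early Algorithm 2 experience as limited and give no count. Assume k such patients join 119, and that their mean HbA1c change differs from Algorithm 1 by d. Ignoring covariate adjustment, the LY3209590 mean shifts by d × k/(119 + k).

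- k = 5: weight 5/124 = 4%; shift 0.008 to 0.024 points for d = 0.2 to 0.6.
- k = 20: weight 20/139 = 14%; shift 0.029 to 0.086.
- k = 60: weight 60/179 = 34%; shift 0.067 to 0.201.

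For scale, the margin is 0.4, and the 90% CI half-width with 119 per arm is 1.645 × 1.1 × √(2/119) = 0.235. Both k and d are assumptions, so the range shows sensitivity and is not an estimate.

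**The case against.** The strongest reply is that pooling was never intended here. The paragraph mentions neither pooling nor Algorithm 2. Where SAP 5.7 and 5.8 want the pooled comparison, they say so. Both estimands refer to the same target population. The SAP's revision history lists the pooled comparison as its own item, while its item on the supportive estimand mentions only the imputation change. The at-least-one-dose wording may simply echo the dose condition in the Efficacy Population. All of this stands, so a reader who infers that the SAP prescribes pooling goes beyond the text. What remains is that the condition, applied as written, does not exclude those patients.

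A reader might also infer that the two results could not be compared, or that the cause of a difference could never be found. The documents do not support that. The endpoint and comparator are shared, and the two planned MMRMs allow the decomposition in step 4 of the working.

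Timing limits the effect too. SAP version 1 was approved on 26 June 2020, before the first patient visit, and amendment (d) on 28 October 2020. That is 124 days, under 18 weeks, so no participant reached Week 26 before the amendment was approved. A full 26-week Algorithm 2 effect is therefore doubtful, although site implementation dates are not given.

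Finally, the fix does not make the two sets identical, because the primary analysis also needs a postbaseline value. That is correct; the fix aligns the LY3209590 group and nothing more.

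**Conclusion.** The point holds as a matter of wording with a consequence for one reported result. As written, the supportive patient set admits dosed Algorithm 2 patients, and the default in SAP 5.1 does not clearly remove them. Followed literally, the supportive estimate would rest on a different LY3209590 group from the primary estimand and the noninferiority claim, and the plan would contain no treatment-policy estimate for Algorithm 1 alone.

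The noninferiority decision, which uses only the primary estimand, and the sample size are untouched. The size of the shift cannot be derived from the documents. It is small if few Algorithm 2 patients were dosed, and any particular percentage of the margin would rest on an assumed count and an assumed difference. This is a free improvement, not an error in the decision rule.

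**What to change.** In the supportive-estimand paragraph of SAP 5.7:

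1. Replace the patient-set phrase with *for the Efficacy Population with non-missing baseline*.
2. Keep the rule that all Week 26 data are used regardless of treatment disposition.
3. State the ANCOVA treatment levels: LY3209590 Algorithm 1 and insulin degludec.
4. If an Algorithm 1 plus Algorithm 2 version is wanted, list it separately as an additional sensitivity analysis, parallel to the pooled MMRM.

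The cost is a few words in the SAP. No new data, no change of sample size and no change to the primary analysis are needed. If the SAP is no longer open to revision, SAP 5.1 allows such a change and its justification to be described in the clinical study report.

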5.8. Secondary and Additional Efficacy Analyses

The primary population for the secondary analysis on HbA1c reduction is the EAS. Treatment comparison at 26 weeks will be used to assess the differences. The 2-sided 90% CI for the LS mean of the differences in the change in HbA1c at 26 weeks will also be constructed.

The following secondary efficacy outcomes will be analyzed based on the EAS using the same MMRM model as the primary analysis with the addition term of HbA1c strata ($<8.5\%$ and $\geq 8.5\%$) for non-HbA1c measures:

1. HbA1c change from baseline to Week 12.
2. Fasting blood glucose (FBG) and change by SMBG from baseline to Week 12 and Week 26;
3. Fasting serum glucose (FSG) by laboratory and change from baseline at Weeks 12 and 26;
4. Between-day glucose variability measured by the SD and the CV of the FBG at Week 12 and 26;
5. Six-point SMBG profile (pre-meal and 2-hour postprandial SMBG measurements for the morning, midday, and evening meals) at Weeks 12 and 26.
6. Within-day and between-day glucose variability measured by the SD and the CV of 6-point SMBG.
7. Prandial insulin dose and change from baseline to Week 12 and 26

For the between-day and within-day glucose variability, the variables will take a log-transformation before performing the MMRM analysis.

The proportion of the patients with HbA1c $<7.0\%$ (or $\leq 6.5\%$) will be analyzed based on the multiple imputation with the following steps: 1) imputing the missing values in the continuous HbA1c by treatment, 2) dichotomizing the “complete” continuous HbA1c into binary based on the threshold, then 3) fitting the logistic regression model at each scheduled post-baseline visit, and 4) using Rubin’s rule to combine the results. In the logistic regression model, the independent variables of treatment, country, baseline HbA1c value will be used.

The above analyses may be repeated to compare LY3209590 (by pooling LY3209590 Algorithm 1 and LY3209590 Algorithm 2) with insulin degludec.

The insulin dose units are different between LY3209590 (mg) and insulin degludec (unit). Therefore, descriptive statistics will be provided for the study insulin dose and the dose change from baseline. A loading dose strategy was used only for the first dose of LY3209590. One third of the loading dose will be used as the baseline dose of LY3209590 in the analysis while the dose of insulin degludec at Week 0 will be used as the baseline dose of insulin degludec. No treatment comparison will be conducted. Two sample t-test will be conducted to assess the change from baseline within treatment group.

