9.2. Sample Size Determination

Approximately 238 participants will be randomized to study treatment (LY3209590 Algorithm 1, and insulin degludec) such that approximately 119 participants will be randomized to each treatment. Assuming a 20% dropout rate, approximately 190 participants will complete the study (approximately 95 participants per treatment group).

The 190 participants who complete the treatment will provide at least 80% statistical power to demonstrate the noninferiority in the change in HbA1c from baseline to 26 weeks for LY3209590 Algorithm 1 versus insulin degludec, based on the following assumptions:

- True mean difference = 0%
- SD of 1.1%
- NIM of 0.4%
- Using 2-sided alpha level of 0.1

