4.3. Exploratory Objectives

To investigate other safety and efficacy measures for LY3209590 for the following endpoints:

1. Insulin dose at baseline and Week 26;
2. Treatment-emergent adverse events (TEAEs);
3. Incidence and rate of hypoglycemia events during the post-treatment follow-up period;
4. Discontinuation of investigational product (IP) due to adverse events (AEs);
5. Clinical laboratory results;
6. Injection site reactions;
7. Insulin dose for prandial and basal insulin during treatment period and follow-up period
8. Liver aminotransferase change from baseline to Weeks 12 and 26;
9. Triglyceride and FFA change from baseline to Weeks 12 and 26;
10. Body weight change from baseline at Weeks 12 and 26;
11. Glucose time in target range, time in hyperglycemia, time in hypoglycemia using CGM

12. Lipids (cholesterol, LDL, HDL, triglycerides)
13. Six-point self-monitoring of blood glucose (SMBG) profiles
14. The frequency of antibody formation to LY3209590;
15. Incidence and percentage of missed doses of LY3209590 and insulin degludec.

5. A Priori Statistical Methods

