(defined as the observed data with collection date before or on the last dose date +10 days). Sensitivity analyses for selected efficacy measures may be conducted on the Randomized Population using the data up to the study treatment discontinuation.

Unless otherwise stated, the safety analyses will be conducted on the safety analyses set based on the Safety Population using all data collected during the study including treatment and follow-up period regardless of the treatment disposition status. The safety measures will be summarized and compared between LY3209590 (by pooling LY3209590 Algorithm 1 and LY3209590 Algorithm 2 data) and insulin degludec. Safety parameters derived from CGM measures will be summarized and compared between LY3209590 Algorithm 1 and degludec.

Unless otherwise specified, the baseline value used for the analyses will be the last non-missing value obtained for each participant prior to or on the date of first study IP dose (or randomization visit date if first dose date is missing). The baseline liver enzyme lab measures will be the average of all assessments prior to and at randomization visit.

All tests of treatment effects will be conducted at a 2-sided alpha level of 0.1, unless otherwise stated, and all confidence intervals (CIs) will be given at a 2-sided 90% level.

Puerto Rico and the United States (US) are always pooled in the analysis, as Puerto Rico will be considered part of US during randomization. All analyses using country in the model will use pooled country, unless otherwise specified. No other pooling of countries is needed.

For continuous measurements, summary statistics will include sample size, mean, median, standard deviation (SD), minimum, and maximum. For certain variables that are considered to be log-normally distributed, the geometric mean and coefficient of variation (CV) will be provided instead.

For categorical measurements, summary statistics will include sample size, frequency, and percentage. Fisher's exact test will be used. Chi-squared test will be used for multi-category variables.

A mixed-model repeated measures (MMRM) model will be used for continuous outcomes with repeated postbaseline measurements to compare treatment arms, unless otherwise noted.

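### SAP 5.8 names a two-sample t-test for the within-arm change in study insulin dose, where the doses are paired

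*SAP*

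**What the plan says.** SAP Section 5.8 handles the study insulin dose separately from the other efficacy measures, because one arm is dosed in mg and the other in units. It plans that "descriptive statistics will be provided for the study insulin dose and the dose change from baseline". It then defines each participant's baseline from that participant's own dosing. For LY3209590, "One third of the loading dose will be used as the baseline dose of LY3209590 in the analysis"; for degludec it is the Week 0 dose. Two short sentences follow: "No treatment comparison will be conducted", and then "Two sample t-test will be conducted to assess the change from baseline within treatment group". No visit is named for the test.

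The endpoint is listed among the exploratory objectives in SAP Section 4.3, item 1: "Insulin dose at baseline and Week 26". Item 7 of the same list also covers basal dose across the treatment and follow-up periods.

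**The concern.** A two-sample t-test compares the means of two independent groups. Here the arms are not being compared, so the only two sets of values left are the baseline and later doses within one arm, and these come from the same people. If the input is instead each participant's change score, there is only one sample per arm and a two-sample test cannot be run. On either reading the named test does not fit its stated purpose.

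A programmer who follows the text would report a within-arm p-value based on the wrong standard error in both arms. One who silently substitutes a paired test would leave an undocumented departure from the SAP.

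**Working it through.** The plan gives no figure for this test, so there is none to reproduce. The check has two parts.

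**Does another section correct the wording?**

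- SAP Section 5.1 mentions a within-treatment p-value for change from baseline, but as part of the MMRM output. Section 5.1 applies the MMRM unless otherwise noted, and Section 5.8 notes otherwise for study dose.
- The dose item in the Section 5.8 MMRM list (item 7) is prandial insulin, a different variable.
- Neither document names a paired or one-sample test for study dose.

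**How large is the error if the test is run as written?**

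Inputs:

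- n = 95 per arm. Protocol Section 9.2 plans "approximately 95 participants per treatment group" after dropout: 119 × 0.80 = 95.2.
- Two-sided alpha 0.1. SAP Section 5.1 sets this for tests of treatment effects; using it for a within-arm test is an assumption.
- Equal SDs s at baseline and later: an assumption.
- Within-participant correlation r: not in the documents, so a range is shown. A positive value is likely, because Protocol Section 10.8 sets each new dose as the previous one plus or minus a step in both arms.

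Formulas:

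- Two-sample standard error: s√(2/n)
- True standard error of the mean change: s√(2(1−r)/n)
- Ratio: 1/√(1−r)
- Actual type I error: 2·P(t_df > t₁₈₈,₀.₉₅ / √(1−r)), where 188 = 2×95 − 2, t₁₈₈,₀.₉₅ = 1.653, and df = 188/(1+r²) is the Satterthwaite value for the pooled variance under correlation

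| r | SE ratio | Effective cut-off (1.653 × ratio) | df | Type I error (nominal 10%) |
|---|---|---|---|---|
| 0.3 | 1.20 | 1.98 | 172.5 | 4.98% |
| 0.5 | 1.41 | 2.34 | 150.4 | 2.07% |
| 0.7 | 1.83 | 3.02 | 126.2 | 0.31% |
| 0.8 | 2.24 | 3.70 | 114.6 | 0.03% |

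Simulation with 200,000 data sets per value of r gave 4.99%, 2.12%, 0.30% and 0.03%. In a separate simulation the paired test held 9.9% to 10.0%.

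The cost in power was simulated for a mean change of 0.2 SD with 95 participants:

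| r | Paired test | Two-sample test |
|---|---|---|
| 0.5 | 62% | 35% |
| 0.7 | 81% | 32% |

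Sensitivity to the assumptions:

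- **Sample size:** from n = 80 to n = 119 the type I error hardly moves (for r = 0.5, 2.09% to 2.06%).
- **Alpha:** at 0.05 the four values are 1.95%, 0.60%, 0.045% and 0.002%.
- **Unequal SDs:** if the later SD is k = 1.5 times the baseline SD, the ratio is √((1+k²)/(1+k²−2rk)). At r = 0.5 this is √(3.25/1.75) = 1.36; over the four values of r it is 1.18, 1.36, 1.68 and 1.96.

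**The case against.** The strongest reply is that this is a label error and not a choice of analysis. The sentence itself gives change from baseline within an arm as its purpose, and the section already treats the dose change as a variable to be summarised. A statistician would probably run a paired test, and the phrase may have been meant as paired or as two-sided. That is plausible, and it limits how confident one can be that a wrong analysis would be run. It does not make the instruction correct.

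The second reply is that little depends on the result. This stands. The endpoint is exploratory, no decision rule uses the p-value, and the error is conservative for positive r. The correct standard error is also recoverable from planned output. SAP Section 5.1 states: "For continuous measurements, summary statistics will include sample size, mean, median, standard deviation (SD), minimum, and maximum". For the dose change, the SD divided by √n is the paired standard error.

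The third reply is that the size depends almost entirely on an assumed r, and that type I error is a weak lens when both arms are titrated to a fasting glucose target and some dose change is expected. This is fair. The firm result is the factor 1/√(1−r) under equal SDs; the percentages illustrate it, and the loss of power is the more practical description.

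Finally, the missing visit is partly covered by Section 4.3, where item 1 names Week 26. Item 7 is broader, so Week 26 should not be read as the only possible time point.

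**Conclusion.** The concern holds: the test is wrong as written, and the severity is minor. Followed literally, SAP Section 5.8 gives an incorrect standard error and p-value for the study-dose change in each arm. For r between 0.3 and 0.8 the standard error is too large by 1.20 to 2.24 times, and a nominal 10% test operates at about 5% down to 0.03%. These figures assume r, equal SDs, alpha 0.1 for this test and 95 participants per arm; of these, r matters most and is unknown. The direction is conservative only if r is positive. The primary HbA1c analysis, the non-inferiority decision and the prandial-dose MMRM are not affected. The unnamed visit is a missing detail that should be settled in the same edit, and the conclusion does not rest on it.

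**What to change.** In SAP Section 5.8, replace the two-sample t-test with a paired t-test (equivalently, a one-sample t-test on each participant's change from baseline), done separately within each treatment group in participants who have both doses. Name the visit or visits tested. Week 26 follows from Section 4.3, item 1; if other time points under item 7 are to be tested, list them too.

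The cost is one phrase and a visit label, with no new data and no new table. Protocol Section 9.4.5 leaves exploratory analyses to the SAP and the protocol describes no test for this endpoint, so a protocol amendment should not be needed. If the SAP is not reissued, the clinical study report should record that a paired test was used.
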